Approach: We propose to conduct an open-label feasibility trial to understand the feasibility of TEA in patients with painful CP. In this open-label study, all subjects will receive TEA at acupoint ST36 in an unblinded manner. This will inform on recruitment & retention rates, percentage of patients with complete data collection and compliance with study procedures. This will also assist in sample size calculations for a future larger study.

Aim 2: To collect pilot data on the efficacy of TEA on abdominal pain, patient reported outcomes, and quality of life, in patients with painful CP. TEA at ST36 has been shown to be effective in the treatment of patients with abdominal pain due to visceral hypersensitivity and pancreatic inflammation.^{10, 15} We will use parameter P100 (100Hz, 0.5ms, 0.1s-on and 0.4s-off, and tolerable current output), which has been found most effective in treating visceral pain in animals and patients with irritable bowel syndrome.^{13, 16} TEA at this acupoint may be effective in ameliorating pain in CP by improving pancreatic inflammation or autonomic function.

3. Methods: participants, interventions, and outcomes

In this study, we aim to assess feasibility of TEA, enrollment methods, and data collection tools. All patients will receive TEA via ST36 twice daily (a point below the knee cap) in an unblinded fashion. We will then use this preliminary data to apply for competitive funding to conduct a larger study. The population, intervention and outcome for this study are summarized in **Table 1**.

Table 1: Summary of study population, interventions, outcomes and setting

Population	Adult subjects aged 18 to 75 years with chronic pancreatitis and abdominal pain
Intervention	Home-based 30-minute sessions of TEA twice a day for 4 weeks
Control	None
Outcome	Enrollment, retention, and data collection feasibility
Setting	Comprehensive pancreas clinic at the University of Michigan

Eligibility criteria:

Inclusion criteria

1. Age 18 to 75 years of age.
2. Diagnosis of chronic pancreatitis, based on a score ≥ 4 using the previously validated Mayo scoring system that uses morphologic and functional criteria¹⁷, or endosonographic features suggestive or consistent with CP based on Rosemont criteria¹⁸.
3. Abdominal pain present at least once a week within the last month
4. Willing and able to provide written informed consent

Exclusion criteria

1. Pregnancy or breastfeeding mother
2. Imprisoned individuals

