3. Comprehensive Pain Assessment Tool Short Form for Chronic Pancreatitis (COMPAT-SF) [timeframe - baseline, 4 weeks from treatment onset, 8 weeks from treatment onset]: The COMPAT-SF is a validated self-reported tool specifically designed for patients with pancreatic disease. The COMPAT-SF carries several sub-scores for pain pattern, pain severity, pain provocation, pain spreading, and pain description. The pain pattern scale ranges from 50-100 with higher scores denoting worse pain. The severity score ranges from 0-100 with higher scores denoting worse pain. The provocation score ranges from 0-70 with higher scores denoting worse pain. The spreading score ranges from 0-90 with higher scores denoting worse pain. The description score ranges from 0-80 with higher scores denoting worse pain. The total score ranges from 15-90 with higher scores denoting worse pain.
4. Number of patients using prescription opioids for pain control at time of assessment [timeframe - baseline, 4 weeks from treatment onset, 8 weeks from treatment onset]: Opioid use (yes/no binary answer) at each assessment.

5. Mean reported daily opioid dose for patients using prescription opioids at time of assessment [timeframe - baseline, 4 weeks from treatment onset, 8 weeks from treatment onset]: Opioid dose (continuous variable in milligrams of morphine equivalent) at each assessment.
6. Overall Quality of Life [timeframe - baseline, 4 weeks from treatment onset, 8 weeks from treatment onset]: Overall quality of life will be assessed using the PROMIS-29 instrument. The PROMIS-29 instrument incorporates 7 domains: physical functioning, fatigue, pain interference, depression, anxiety, ability to participate in social roles and activities, and sleep disturbance. Each of these domains have a score 0-40 with higher scores representing worse quality of life in these domains. There are also 2 summary scores: Physical Health and Mental Health. Z-scores are calculated for these two summary scores with lower scores representing better quality of life.
7. Change from baseline on the Hospital Anxiety and Depression Scale (HADS) [timeframe - baseline, 4 weeks from treatment onset, 8 weeks from treatment onset]: The HADS is a validated self-reported tool that screens for symptoms of anxiety and depression. Possible scores range from 0 to 21 (higher scores reflect more severe symptoms of anxiety or depression).

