All data will then be captured in a password-protected database through Redcap. Several methods will be used to promote data quality and integrity including database development, proper training of study team members, and use of data quality rules and validation. Each subject will be assigned a unique random number, and Protected Health Information will be coded to

ensure no one outside the study team will be able to identify a subject's identity. This database will be stored in a password-protected database, in a password-protected folder on a secure server behind the University of Michigan firewall. The information will, at all times, only be able to be accessed by the study investigators.

F. After enrollment is completed, study subjects who enrolled and received TEA will be reached out via a phone call to assess on global impression and acceptability of the treatment. Study subjects will be asked the following questions in relation to the use of TEA on their chronic pancreatitis pain.

- Patient global impression of change (PGIC): this is a 1-item question that should take less than 1 minute
- Modified abbreviated acceptability rating profile: this is an 8-item questionnaire that should take 2 minutes (Tarnowski KJ, Simonian SJ. Assessing treatment acceptance: the Abbreviated Acceptability Rating Profile. *J Behav Ther Exp Psychiatry* 1992;23:101-6).
- Two open questions: (i)“How did the TEA device help you in managing your pancreatitis pain?” and (ii)“What modifications would you suggest to improve the TEA treatment?”

5. Statistical methods

Sample size calculation

We will conduct an open-label pilot study of 10 subjects with CP that fulfill eligibility criteria and that receive the TEA device during visit 1. This will serve to inform feasibility on enrollment, adherence, retention, and completion of data collection. Data obtained in this study will lead to protocol changes for a larger randomized controlled trial that we will plan in the future. The study will be under powered to address any clinical outcomes. We anticipate attrition of approximately 10% for a study of this nature.

Statistical analysis

All analyses will be performed according to the intention-to-treat principle. All primary outcomes will be measured using descriptive statistics as absolute values (percentage), mean \pm standard deviation (SD), and median (interquartile range [IQR]), as appropriate.

Primary outcomes

A. Enrollment feasibility:

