- Proportion of approached participants who meet eligibility criteria.
- Proportion of those who meet eligibility criteria and who provide informed consent
- Proportion of participants who meet the criteria after the run-in period among those who provided informed consent.
- Proportion of participants who start the intervention among those who meet run-in period criteria.

- B. Adherence: proportion of participants who adhere to the intervention as prescribed among those who start the intervention
- C. Retention feasibility: proportion of patients who complete follow up visit at 4 weeks and return complete follow-up questionnaires at week 8, among those who started the intervention
- D. Visit duration:
 - For visit 1, median (IQR) of the time that takes to complete visit 1.
 - For visit 2, the median (IQR) of the time that takes to complete visit 2.
- E. Data collection feasibility:
 - Proportion of participants who come for visit 1 and complete all the surveys involved in the study.
 - Proportion of study surveys that are completed per protocol

Exploratory endpoints

- Worst pain on visual analogue scale
 - Mean \pm SD of worst pain during the run-in period (baseline)
 - Mean \pm SD of worst pain during the treatment period (week 0-4)
 - Mean \pm SD of worst pain during the last week of treatment (week 4)
 - Mean \pm SD of worst pain after completion of treatment (week 5-8)
 - Mean \pm SD of worst pain during the last week without treatment (week 8)
 - Mean difference of worst pain score from the last week of treatment compared to baseline worst pain.
 - Rank-sum test or paired t test depending on data distribution to compare worst pain score from the last week of treatment compared to baseline worst pain.
 - Mean difference of worst pain score after completion of treatment compared to worst pain during the last week of treatment
 - Rank-sum test or paired t test depending on data distribution to compare worst pain score after completion of treatment compared to pain severity from the last week of treatment.
- Average pain on visual analogue scale
 - Mean \pm SD of average pain during the run-in period (baseline)
 - Mean \pm SD of average pain during the treatment period (week 0-4)
 - Mean \pm SD of average pain during the last week of treatment (week 4)
 - Mean \pm SD of average pain after completion of treatment (week 5-8)
 - Mean \pm SD of average pain during the last week without treatment (week 8)

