- Rank-sum test or paired t test depending on data distribution to compare pain severity after completion of treatment compared to pain severity from the last week of treatment.
- Pain by COMPAT-SF
 - Mean \pm SD of COMPAT-SF score at onset of treatment (at baseline during visit 1)
 - Mean \pm SD of COMPAT-SF score at end of treatment (at 4 weeks during visit 2)
 - Mean \pm SD of COMPAT-SF score at end of follow-up without treatment (at 8 weeks)
 - Mean difference of COMPAT-SF score from end of treatment compared to score at baseline.
 - Rank-sum test or paired t test depending on data distribution to compare COMPAT-SF score from end of treatment compared to baseline score

- Mean difference of COMPAT-SF score at end of follow-up without treatment compared to score at baseline
- Rank-sum test or paired t test depending on data distribution to compare COMPAT-SF score from end of follow-up without treatment compared to baseline score
- Mean difference of COMPAT-SF score at end of follow-up without treatment compared to score at end of treatment
- Rank-sum test or paired t test depending on data distribution to compare COMPAT-SF score from end of follow-up without treatment compared to score at end of treatment
- Proportion of patients using opioids
 - Proportion of patients using prescription opioids for pain control at onset of treatment (at baseline during visit 1)
 - Proportion of patients using prescription opioids for pain control at end of treatment (at 4 weeks during visit 2)
 - Proportion of patients using prescription opioids for pain control at end of follow-up without treatment (at 8 weeks)
 - McNemar Test to compare proportion of patients using opiates at end of treatment compared to baseline
 - McNemar Test to compare proportion of patients using opiates at end of follow-up without treatment compared to baseline
 - McNemar Test to compare proportion of patients using opiates at end of follow-up without treatment compared to end of treatment
- Reported dose of opiates by milligrams of morphine equivalent (MME)
 - Mean \pm SD of MME at onset of treatment (at baseline during visit 1)
 - Mean \pm SD of MME at end of treatment (at 4 weeks during visit 2)
 - Mean \pm SD of MME at end of follow-up without treatment (at 8 weeks)
 - Mean difference of MME from end of treatment compared to baseline.
 - Rank-sum test or paired t test depending on data distribution to compare MME from end of treatment compared to baseline

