 - Rank-sum test or paired t test depending on data distribution to compare mental QOL from end of follow-up without treatment compared to mental QOL at end of treatment
- Hospital anxiety and depression scale (HADS)
 - Mean \pm SD of HADS score at onset of treatment (at baseline during visit 1)
 - Mean \pm SD of HADS score at end of treatment (at 4 weeks during visit 2)
 - Mean \pm SD of HADS score at end of follow-up without treatment (at 8 weeks)
 - Mean difference of HADS score from end of treatment compared to baseline.
 - Rank-sum test or paired t test depending on data distribution to compare HADS score from end of treatment compared to baseline
 - Mean difference of HADS score at end of follow-up without treatment compared to baseline
 - Rank-sum test or paired t test depending on data distribution to compare HADS score from end of follow-up without treatment compared to baseline
 - Mean difference of HADS score at end of follow-up without treatment compared to HADS score at end of treatment
 - Rank-sum test or paired t test depending on data distribution to compare HADS score from end of follow-up without treatment compared to HADS score at end of treatment
- Pancreatitis related hospitalizations
 - Proportion of patients who had a pancreatitis related hospitalization during the treatment period

- Proportion of patients who had a pancreatitis related hospitalization during the follow up period without treatment
- Proportion of patients who had a pancreatitis related hospitalization during the study period
- Adverse events
 - Proportion of patients who had an adverse event due to the intervention
- Patient Global Impression of Change
 - Proportion of patients who consider their pain improved (PGIC ≤ 3)
- Treatment acceptability
 - Proportion of patients who agree or strongly agree that the treatment was an acceptable intervention for dealing with chronic pancreatitis pain

For missing data, we will use multiple imputation methods. Statistical significance will be defined as $P < 0.05$.

6. Safety management

Safety monitoring

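### Exploratory endpoints only: the non-parametric option for the within-patient comparisons is the rank-sum test, which assumes two independent samples; it should be the Wilcoxon signed-rank test

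*Combined protocol and SAP*

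**What the plan says.** The trial is single-arm. The approach to Aim 1 in Section 2 states that "all subjects will receive TEA at acupoint ST36 in an unblinded manner", and Table 1 in Section 3 lists no control.

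Under Exploratory endpoints in Section 5, the tested continuous endpoints share one formula. For the worst-pain scale it is "Rank-sum test or paired t test depending on data distribution to compare worst pain score from the last week of treatment" against baseline. For the pancreatitis pain tool it is "Rank-sum test or paired t test depending on data distribution to compare COMPAT-SF score from end of treatment compared to baseline score", and for anxiety and depression "Rank-sum test or paired t test depending on data distribution to compare HADS score from end of treatment compared to baseline". The same formula serves average pain, both BPI-SF scores, opioid dose, and physical and mental quality of life.

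For the binary endpoint, opioid use, the plan names a paired test: "McNemar Test to compare proportion of patients using opiates at end of treatment compared to baseline".

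The end of Section 5 sets significance at P < 0.05. The signed-rank test is not named anywhere.

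**The concern.** With one arm, every tested comparison over time is within patient. Two of the three tests in the plan (paired t, McNemar) respect this. The rank-sum test does not: its null distribution assumes that the scores at the two times come from separate, independent groups. An analyst who follows the text, and judges the data unsuitable for the t test, would run a test that does not fit the design. An analyst who silently substitutes the signed-rank test would depart from the written plan.

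At stake is the validity of the exploratory P values whenever the rank option is used. Those values matter somewhat, because Aim 2 is to collect pilot efficacy data and the study is meant to inform a larger randomized trial. No sample size, primary result or point estimate depends on them.

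**Working it through.** **1. Extent.** Listings of the formula in Section 5:

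| Endpoint | Listings |
|---|---|
| Worst pain, average pain, BPI-SF severity, BPI-SF interference | 4 × 2 = 8 |
| COMPAT-SF, opioid dose, physical QOL, mental QOL, HADS | 5 × 3 = 15 |
| Total | 23 |

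One listing under BPI-SF interference repeats the severity wording. All 23 name the rank-sum test.

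**2. Inputs.** From Section 5: 10 patients; about 10% attrition, so 10 × 0.9 = 9 pairs; significance at 0.05 (taken as two-sided, since sidedness is not stated). The documents give no within-patient correlation, SD or effect size. Correlations of 0.3, 0.5 and 0.7 are assumptions. The plan states no figure that depends on this test, so there is none to reproduce.

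**3. Direction of the error.** Let both times have variance σ² and correlation ρ. The variance of the mean change is 2σ²(1 − ρ)/n, whereas an independent-samples test works as if it were 2σ²/n. The ratio of true to assumed variance is 1 − ρ, that is 0.7 / 0.5 / 0.3 for ρ = 0.3 / 0.5 / 0.7. The test overstates the noise and rejects too rarely. The rank version behaves in the same way.

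**4. Size of the error in the rank test itself.** Simulation under no change, 40,000 replicates per cell (Monte Carlo standard error about 0.1 percentage point at 5%). The tests are run on all simulated data sets, at a nominal 5%:

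| Setting | Test | ρ = 0.3 | 0.5 | 0.7 |
|---|---|---|---|---|
| Continuous, n = 10 | Rank-sum, exact | 1.9% | 0.9% | 0.2% |
| | Signed-rank, exact | 4.9% | 4.9% | 4.9% |
| Continuous, n = 9 | Rank-sum, exact | 1.8% | 0.8% | 0.2% |
| | Signed-rank, exact | 3.9% | 3.9% | 3.9% |
| Integer 0–21, n = 10 | Rank-sum, tie-corrected approximation | 2.0% | 0.9% | 0.2% |
| | Signed-rank, exact, zeros dropped | 4.3% | 4.1% | 3.9% |
| | Signed-rank, normal approximation | 4.8% | 4.8% | 4.9% |

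The signed-rank level at n = 10 is known exactly: 50/1024 = 4.88%. The integer rows use the HADS range ("Possible scores range from 0 to 21") with an assumed mean of 8 and SD of 4.

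**5. Size of the error over the whole rule.** The plan does not say how the distribution will be judged. Assume a Shapiro–Wilk test at 5% on the differences, with n = 10:

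| Data | Share sent to the rank test | As written (ρ = 0.3 / 0.5 / 0.7) | With signed-rank |
|---|---|---|---|
| Normal | 5% | 4.8% / 4.7% / 4.8% | 5.0% / 4.9% / 5.0% |
| Integer 0–21 | 6–8% | 4.9% / 4.8% / 4.6% | 5.0% / 5.1% / 5.0% |

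The change is 0.2 percentage points for normal data and 0.1 to 0.4 for the 0–21 scores. With strongly skewed data more data sets reach the rank test and the effect is larger. How much larger depends on a degree of skew that the documents do not give.

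**6. Illustration.** Take ten made-up patients with baseline scores from 4.5 to 9, all improving by between 0.6 and 1.4 points. The rank-sum test gives P = 0.165 and the signed-rank test P = 0.002. Here the spread between patients hides a change that every patient shows. The correlation in this example is 0.99, so it is an extreme case.

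**The case against.** **It is probably a slip of the pen, with almost no consequence.** The test sits beside a paired t test, opioid use gets McNemar, and there is only one arm, so paired analysis is clearly intended. Step 5 shows how little changes when data are near normal. All of this stands and is why the point is minor. It does not remove the point: the same words recur 23 times and nothing in the plan overrides them.

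**A distribution check beside a paired t test is ordinarily a check on the differences.** This also stands. Saying so in the plan is a clarification, not the correction of an error.

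**The signed-rank test will not always have more power.** This is correct. For normal data and a 0.5 SD shift at n = 10, rank-sum power is 13% / 10% / 8% at correlation 0.3 / 0.5 / 0.7, against 22% / 29% / 43% for signed-rank. For strongly skewed (log-normal) data with a location shift, the order can reverse. The case for the change is that the test should fit the design.

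**Stronger readings that the documents do not support.** A reader might infer that the plan risks false positive claims of efficacy. With positive correlation, which is to be expected for repeated scores in one patient, the error goes the other way; only negative correlation would inflate it (7.1% at −0.3, normal data, n = 10). A reader might also infer that the trial's main conclusions are at risk. The primary outcomes are feasibility measures reported descriptively, without tests, and Section 5 says that the study is underpowered for clinical outcomes.

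**Conclusion.** The concern holds as a minor error of wording, limited to the exploratory endpoints. As written, the rank option does not fit a single-arm, within-patient design, and its P value is not valid against 0.05. Used on its own at n = 10, it has a true type I error of about 1.9% / 0.9% / 0.2% where the exact signed-rank test has 4.9%. Over the whole choice between tests, the effect is negligible for near-normal data and larger for skewed data.

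These sizes rest on assumed positive correlations, an assumed switching rule and two-sided testing. No excess of false positives and no general gain in power is claimed. Descriptive summaries, mean differences and primary outcomes are unaffected.

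**What to change.** In all 23 listings under Exploratory endpoints in Section 5, replace the rank-sum test with the Wilcoxon signed-rank test on within-patient differences. State once that the choice between it and the paired t test rests on the distribution of those differences. It would help to add how zero differences and ties are handled, since several endpoints are integer scores.

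The cost is an edit to the statistical section before analysis. It needs no extra data, visits or patients.

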The treatment will be discontinued if the patient develops an adverse event (discussed under *6. Safety Management*) that requires the treatment to be stopped or at the participant request. Subjects will be allowed to start and continue conventional medical therapy for the duration of the study, including any pain medications. This will be at the discretion of the treating physician. This will allow us to assess the addition of TEA to conventional care. The TEA intervention will be discontinued if the patient gets admitted to hospital or if a surgical or endoscopic procedure is performed during the treatment phase of the study. During the 4 weeks of treatment, subjects will complete pain diaries through RedCap. This will take 2 minutes for completion.

IV. Monitoring phone calls

To assess any potential problems with the TEA device, we will contact participants via telephone within 72 hours of starting treatment and then weekly at 1 week, 2 weeks, and 3 weeks from treatment initiation.

V. Visit 2 (V2), 4 Weeks from V1

During this follow-up period subjects will complete the same set of surveys that was completed during the first visit to assess pain, quality of life, and anxiety or depression. Subjects will also return the TEA device using their return mailer (provided during or prior to visit 1). In the event the device is broken or non-functional, participants will still be requested to return the device.

VI. Visit 3 (V3), at 8 weeks from V1

After subjects finish treatment (4 weeks from V1), they will continue completing daily pain diaries for additional 4 weeks. During this phase, subjects will not receive device stimulation. At 8 weeks from V1, subjects will be asked to complete the same set of surveys completed during visit 1 and 2. These will be completed via RedCap.

VII. Close-out phone call, at end of trial

At the end of the trial, study subjects who enrolled and received TEA will be reached out via a phone call to assess on global impression and acceptability of the treatment.

Outcomes

Primary outcomes

1. Enrollment feasibility: how many patients with CP who are assessed meet eligibility criteria. In addition, of these, how many provide informed consent. Of those who consent, how many meet criteria to participate after the run-in period. Of those who meet run-in period criteria, how many start the intervention (TEA).

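### The multiple-imputation rule is not limited to exploratory endpoints, so read literally it would fill in primary adherence for a patient whose device log is not recovered

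*Combined protocol and SAP*

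**What the plan says.** Section 5 (Statistical methods, Statistical analysis) opens with "All analyses will be performed according to the intention-to-treat principle" and closes with "For missing data, we will use multiple imputation methods". The closing sentence names no variables, no imputation model, no level (item, day or period mean), no number of imputations and no exceptions.

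The primary outcomes are descriptive feasibility measures. Adherence is the "proportion of participants who adhere to the intervention as prescribed among those who start the intervention". According to section 3 (Home-based treatment period), the device itself records when, for how long and at what intensity it is used. Patients send it back at Visit 2 by prepaid mailer. The plan foresees faults: "In the event the device is broken or non-functional, participants will still be requested to return the device". It does not say how adherence is scored when no log can be read.

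Retention is a proportion of those who start treatment, and the first survey-completion measure is a proportion of those who attend visit 1. The diary endpoints are means over set periods.

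**The concern.** Adherence is one of the main results the study exists to produce, because the plan says its data will shape a later randomized trial. A patient who stops early because of discomfort, a hospital admission or a procedure may be less likely to return the device, and is also likely to have used it less. Filling in that patient's adherence from those who returned theirs assumes the two groups behaved alike. If they did not, the reported figure is too high.

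For the exploratory scores the sentence leaves the model open. With about 10 patients, the choice of model largely determines the imputed values. Missing items are also to be expected, since section 6 lets participants skip questions that cause discomfort.

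**Working it through.** **Inputs from the plan.** Sample size: "We will conduct an open-label pilot study of 10 subjects with CP". Attrition: "We anticipate attrition of approximately 10% for a study of this nature". Diary length: 2 + 4 + 4 weeks (section 3, Participant timeline). Diary entries: two pain scores a day (Exploratory outcomes, item 1). Diary endpoints: five period means per scale (section 5).

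**Assumptions, not in the plan.** The number of adherent patients, and that the log is available only from the recovered device.

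**The plan's own figure.** 2 + 4 + 4 = 10 weeks, as stated. That is 10 × 7 = 70 days, and 70 × 2 = 140 entries per patient. Item 1 of the exploratory outcomes also says the diary runs until eight weeks after the intervention ends. Read literally this is 2 + 4 + 8 = 14 weeks, or 98 days. The Participant timeline and section 4, item B, give four weeks after treatment.

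**How often someone is lost.** The expected number is 10 × 0.10 = 1. If losses are independent:
- P(at least 1) = 1 − 0.9^10 = 0.65
- P(at least 2) = 1 − 0.9^10 − 10 × 0.1 × 0.9^9 = 0.26

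These are patients lost, which is not the same as logs lost.

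**Adherence.** Let m of 10 logs be missing and a of the other 10 − m patients be adherent. Imputation that borrows the observed proportion gives on average [a + m × a/(10 − m)]/10 = a/(10 − m). Counting missing logs as not adherent gives a/10. The upper bound is (a + m)/10.

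| Missing logs | Adherent among observed (assumed) | Imputed | Missing = not adherent | Upper bound |
|---|---|---|---|---|
| 1 | 8 of 9 | 88.9% | 80% | 90% |
| 2 | 7 of 8 | 87.5% | 70% | 90% |

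The exact 95% interval for 8/10 is 44.4% to 97.5%.

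**Retention and survey completion.** Every starter either did or did not complete, so no value is missing. One non-completer gives 9/10 = 90% retention (exact 95% interval 55.5% to 99.7%).

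**Diary.**
- An unrestricted normal model for 70 days of one scale has 70 + 70 × 71/2 = 2,555 parameters. For both scales it has 140 + 140 × 141/2 = 10,010. The sample covariance from 10 patients has rank at most 9. Regressing one day on the other 69 leaves 10 − 70 = −60 residual degrees of freedom. This model cannot be estimated.
- A model for the five period means of one scale has 5 + 15 = 20 parameters. Each regression leaves 4 residual degrees of freedom with 9 complete patients, or 5 with 10. This is estimable but fragile.
- A random-intercept model on the daily values converged in 100 of 100 simulated datasets. The simulation assumed between- and within-patient SDs of 1.5, 10% of days missing at random, and one patient lost after day 28.

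**The case against.** The strongest reply is that this is loose wording in a descriptive pilot. Several parts of that reply stand.

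- A reader might infer that the plan will impute retention and survey completion and so push them towards 100%. It does not say so. The definitions leave no missing status, and a careful analyst would impute nothing there.
- A reader might infer that diary imputation is impossible. That is true only of the unrestricted day-by-day model, which the plan never proposes. It analyses period means, and constrained models can be fitted.
- A reader might equate a missing log with non-adherence. A broken device gives an unknown value, and the prepaid mailer and the request to return faulty devices both make missing logs less likely. A patient who drops out may still return the device, and a completer's device may fail.
- The 89% against 80% gap is one patient, rests on assumed counts, and lies well inside the exact interval. The plan sets no adherence target, so no stated decision turns on it. The efficacy results are exploratory, and the plan says: "The study will be under powered to address any clinical outcomes".

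The reply does not remove the gap for adherence. The rule has no exceptions, and adherence is a primary outcome that can be truly unknown for someone who started treatment.

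**Conclusion.** The point holds for adherence, and more weakly for the exploratory scores. Followed literally, the rule replaces an unrecovered log with a value borrowed from patients who returned theirs. In the illustration this moves adherence by about 9 percentage points with one missing log (88.9 − 80) and 17.5 with two (87.5 − 70), relative to counting the missing patients as not adherent. These are differences between two ways of scoring the same data, not an estimate of bias. Whether the imputed figure is too high depends on how the missing patients actually behaved. They also depend on the assumed counts and on the log being available only from the recovered device.

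For the exploratory scores the defect is reliance on an unnamed model with 9 or 10 patients. The documents do not support a complete ban on imputation. The matter should be settled before analysis; its impact is moderate.

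**What to change.** Replace the closing sentence on missing data with four statements.

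1. Feasibility outcomes are not imputed. All starters stay in the denominators for adherence and retention, and survey completion keeps the denominator the plan gives it. Not completing Visit 2, the week-8 forms or the surveys counts as not achieved.
2. Adherence is reported with missing logs counted as not adherent, beside the observed-log figure and the upper bound. Missing logs due to dropout and to device failure are listed separately.
3. Diary endpoints use the mean of available days in each window, with a minimum number of days stated in advance for each window. Comparisons are paired on observed data, with the number of contributing patients shown. The text should say how this sits with the intention-to-treat statement.
4. Any multiple imputation of exploratory scores is a sensitivity analysis only, with the variables, level and constrained model named.

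The diary length in Exploratory outcomes, item 1, must also be reconciled with the Participant timeline and section 4, item B.

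The cost is SAP wording. The adherence figure may be slightly less favourable, and patients with too little data drop out of the exploratory paired comparisons.
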